##### 4.3.4.c. MRI Screening Document

Each subject will be screened for MRI safety first during the pre-screening process (see section [4.3.1 Pre-Screening Subjects](#)). At the initial screening visit, the subject will fill out an MRI screening document provided by the research team to ensure their safety and comfort in the MRI scanner.

##### 4.3.4.d. Tanner Stage Questionnaire

Each subject will complete a sex-specific pubertal self-assessment questionnaire to assess pubertal development (Tanner Stage; 46). Subjects will complete this in private without parental assistance and will be asked to complete the assessment from memory and to avoid examining themselves.

##### 4.3.4.e. Maximal Exercise Test

Each subject will complete a maximal exercise test on an upright cycle ergometer. Subjects will be fitted with a mask or mouthpiece to measure oxygen consumption ( $VO_2$ ) and carbon dioxide production ( $VCO_2$ ), and a 3-lead electrocardiogram (ECG) to measure heart rate. Following a 2-minute warm-up at 60-70

revolutions per minute (RPM) at 25 Watts, exercise intensity will increase 25 Watts every 2 minutes until the subject can no longer maintain  $\text{RPM} \geq 55$  for more than 5 seconds despite strong verbal encouragement. Average duration of maximal exercise testing in adolescents is approximately 8-12 minutes (45, 48).

#### 4.3.4.f. Cognitive Tests

Table 1 details the cognitive domains being assessed, the specific cognitive abilities, and the tests being performed.

**Table 1. Neuropsychological Evaluation.**

Domain	Ability	Tests
Intelligence	Verbal Functioning	WASI (Verbal IQ)
Intelligence	Nonverbal Functioning	WASI (Performance IQ)
Memory	Verbal memory	NIH Toolbox (List Learning)
Speed Function	Psychomotor speed	NIH Toolbox (Oral Symbol Digit Test)
Executive Function	Inattentiveness/inhibition	NIH Toolbox (Flanker Inhibitory Control and Attention)
Speed Function	Psychomotor speed	NIH Toolbox (Pattern Completion)
Memory	Visual memory	NIH Toolbox (Picture Sequence)
Memory	Visual memory	WRAML (Picture Memory)
Executive Function	Problem solving	D-KEFS (Color-Word Interference)
Executive Function	Divided attention	D-KEFS (Trail Making Test)
Psychiatric Quality of Life	Social-Emotional Functioning	PedsQL - (Child 8-12/Teen 13-18)
Psychiatric Quality of Life	Social-Emotional Functioning	Parents: -CBCL (Child 6-18) -BRIEF-II (Child 6-18) -PedsQL (Child 8-12/Teen 13-18)

These tests will be administered by trained personnel and/or pediatric neuropsychologists via computer, paper forms, and interview as appropriate.

#### 4.3.4.g. Magnetic Resonance Imaging (MRI)

Images will be acquired on a GE 750 3T MRI system located in the WIMR or the Waisman Center. The scanner is located in the WIMR within the UW Department of Radiology or at the Waisman Center Imaging Core. The research team will be administering the scans, as well as processing and analysis of

the data. No contrast agent will be used. While in the scanner, subjects will be monitored for vital signs (see section [4.3.4.m Subject Monitoring](#)). All MR scanners currently used at the University of Wisconsin stay within FDA guidelines and have received FDA approval for use in humans. All pulse sequences used in this study are designed to stay within the current guidelines for dB/dt established by the FDA.

The software and head coil used in this study are not intended for use in the diagnosis or treatment of subjects, nor are they being assessed for safety or efficacy as part of this study. Study data will not be submitted to the Food and Drug Administration (FDA) in support of labeling changes for these devices.

PC VIPR will be utilized to acquire volumetric data sets with three-directional velocity encoding and high spatial resolution in fairly short scan times. This technique has been developed over the last 10 years in the Departments of Medical Physics and Radiology, and has been used and validated in several hundred subjects and have been used with regularity by the medical imaging researchers collaborating on this IRB proposal ([name]). We will also conduct ASL perfusion scans. These methods are well-characterized and used routinely during collaborative studies between Drs. [name] and [name].

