### 4.3.3. Study Visits

Duration: Approximately 6.5-8 hours total.

The study involves 2-3 visits to the WIMR, Waisman Center, or UW Hospital (see section [4.2 Research Sites](#)). Because the data collected in each visit is not dependent on the other visit in a temporal manner, the study visits can occur in any order (i.e. one visit does not need to occur before another). Additionally, the flexibility of conducting study visits in any order allows enhanced scheduling opportunities for subjects and staff.

The “Cognitive Testing” and “MRI Structural Scanning” study visits (see section [4.3.3.a Cognitive Testing Visit](#) and [4.3.3.b MRI Structural Scanning Visit](#)) may occur together or independently as best suited for the subject and research staff. This flexibility allows the potential for the reduction in the number of study visits or the reduction in the time spent at a single visit.

A visit reminder will be provided to potential subjects via phone or email at least 24 hours prior reminding them of the following (see Sections [4.2. Research Sites](#) and [4.3.4.b. Fasting, and Caffeine, NSAID and Exercise Restriction](#)):

- Location of visit (with general campus directions)
- Fasting directions
- Caffeine, NSAIDs, and exercise restriction

Subjects will arrive fasted prior to study visits. Parent(s)/guardian(s) will be encouraged but not required to be present during the study visits (exception: cognitive testing visit).

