## 8. STATISTICAL CONSIDERATIONS

Covariates for all analyses include sex, age, adiposity, aerobic fitness, and education unless noted otherwise.

The overarching statistical approach uses multiple regression to determine whether IR is inversely associated with outcome measures in Aims 1 and 2 and to assess mediation in Aim 3. Mean/summed outcomes (total cognition, total CBF or CP) will be predicted by HOMA-IR, for example. Not only is a composite measure calculated as a mean more reliable than the subdomain scores, but averaging multiple measures of a single construct yields a more powerful hypothesis test than using variables individually (40), under conditions we expect to hold here. This approach avoids inflation of Type I error rate as each hypothesis test examines the relationship among single variables or composites, not among multiple subdomain measures. If the test of the mean or composite score is significant, then there is no increased Type I error rate incurred in subsequent subdomain/regional tests (41).

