### 8.1. MRI Data Processing

Standard and validated tools will be used for image processing. The research team is expert in analyzing brain imaging data and have published several studies focused on MRI-derived blood flow-based measures.

Maps representing gray matter probability and cerebral blood flow will be generated using SPM, FSL, or similar software. Scans will be processed using the most up to date and recommended processing scheme, including methods previously used by our research group and collaborators.

We expect to use standard viewing software (Advanced Workstation 4.3, GE Healthcare) for magnetic resonance angiography and phase contrast data, in addition to

- 1) MIMICS and EnSight, commercial software packages commonly used in 4D flow visualization and
- 2) MatLab-based software for quantitative analysis of 4D data sets

Quantitative data from two 4D multi venc flow acquisitions will be available. The data includes:

- 1) Quantitative blood flow values (peak and mean flow, peak and mean velocity, pulsatility and resistance index) of 4D PC
- 2) Quantitative morphological data (vessel diameter) of:
  - a. Standard magnetic resonance angiography techniques
  - b. 4D PC

### 8.2. Aim 1

Composite scores will be computed by calculating and averaging z-scores within each cognitive domain. Composite total cognitive scores will be predicted from HOMA-IR and the covariates. Pilot data yielded a partial correlation of -0.6 between HOMA-IR and the total cognitive score. A one-tail test of the population correlation coefficient with a Type I error rate of 0.05 requires a sample size of **N=13** to yield power of 0.80. If this composite score test is significant, similar analyses will be performed to examine the relationship between HOMA-IR and individual cognitive ability subdomain scores.

### 8.3. Aim 2

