#### 8.3.2. Aim 2A

Total CVC will be predicted from HOMA-IR and the covariates (intracranial volume is an additional covariate for CVC analyses). Resting CP data indicate reduced perfusion in several anterior brain regions. Pilot data yielded a correlation between HOMA-IR and resting  $\text{CVC}_{\text{MICRO}}$  of  $-0.324$ , such that a sample of size **N=55** will yield the power of 0.8 in a one-tailed test of the correlation, with Type I error rate of 0.05. In contrast, we will test, but do not expect, resting  $\text{CVC}_{\text{MACRO}}$  to be related to HOMA-IR, since resting  $\text{CVC}_{\text{MACRO}}$  is similar in low and high IR.

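### MRI may be done at either of two locations, but nothing in the plan accounts for scanner in the between-subject resting CVC analyses (Aims 2A and 3A)

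*Combined protocol and SAP*

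**What the plan says.** Section 4.2 lists MRI under both WIMR and the Waisman Center. Section 4.3.4.g names one scanner model for the two places: "Images will be acquired on a GE 750 3T MRI system located in the WIMR or the Waisman Center", and then "The scanner is located in the WIMR within the UW Department of Radiology or at the Waisman Center Imaging Core". Section 4.3.3 adds: "The study involves 2-3 visits to the WIMR, Waisman Center, or UW Hospital". No section says how a subject is assigned to a location, how many are expected at each, or whether a subject stays at one.

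Section 8 fixes the adjustment set: "Covariates for all analyses include sex, age, adiposity, aerobic fitness, and education unless noted otherwise". Section 8.3.2 extends it for the flow and perfusion outcomes: "intracranial volume is an additional covariate for CVC analyses". Sections 8.3.3 and 8.4 add no further covariate. On image processing, section 8.1 says "Scans will be processed using the most up to date and recommended processing scheme" and mentions no cross-calibration or harmonisation between scanners.

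Two further passages decide where scanner can matter. Section 4.3.3.c places the pre-glucose baseline and all post-glucose scans in one visit. Section 4.3.3.b allows ASL and PC VIPR also at the separate structural visit. Section 8.3.3 defines the change in CVC as peak during the OGTT minus resting CVC, without saying which visit supplies the resting value.

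**The concern.** Two scanners of the same model need not give identical quantitative ASL or 4D-flow values, and the documents offer no evidence that these two do. Resting CVC is an absolute level compared across subjects, so any difference in level between scanners goes straight into it. In Aim 2A the difference inflates the residual variance. In Aim 3A it acts through the same HOMA-IR-to-CVC path and also as measurement error in the mediator.

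Aim 2A has the least room for this. It sets the overall N of 55, for which section 8.3.2 says the design "will yield the power of 0.8 in a one-tailed test of the correlation, with Type I error rate of 0.05". If scanner use also happened to go with HOMA-IR, the coefficient itself would move, in either direction, and a one-tailed test is sensitive to a shift in the hypothesised direction.

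**Working it through.** **Inputs from the documents.** Aim 2A: pilot r = −0.324, N = 55, one-tailed α = 0.05, power 0.8 (section 8.3.2). Aim 3A: r = 0.37 between resting microvascular CVC and cognition (section 8.4), with stated power 0.9 at N = 55 (section 8.5).

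**Assumptions, not in the documents.** The scanner offset d is 0.25 to 0.75 SD of resting CVC. The share p of subjects on the second scanner is 0.5, with 0.2 as an alternative. The correlation φ between scanner and HOMA-IR is 0, or ±0.2 for illustration.

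**Step 1: the plan's figures.** For a one-tailed test of a correlation by the noncentral t distribution (df = n − 2, noncentrality = √n · r/√(1 − r²)), r = 0.324 at n = 55 gives power 0.806, and 55 is the smallest n that reaches 0.80. The stated N is reproduced. For r = 0.37 at n = 55 the power is 0.898, matching the stated 0.9.

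**Step 2: offset unrelated to HOMA-IR.** The offset adds variance p(1 − p)d², so the correlation becomes r/√(1 + p(1 − p)d²). For example, with d = 0.75 and p = 0.5: 0.324/√(1 + 0.25 × 0.5625) = 0.324/1.068 = 0.303.

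| Offset d (SD) | Aim 2A r, 50:50 | Power, 50:50 | Aim 2A r, 80:20 | Power, 80:20 |
|---|---|---|---|---|
| 0 | 0.324 | 0.81 | 0.324 | 0.81 |
| 0.25 | 0.321 | 0.80 | 0.322 | 0.80 |
| 0.50 | 0.314 | 0.78 | 0.318 | 0.79 |
| 0.75 | 0.303 | 0.75 | 0.310 | 0.77 |

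The 50:50 split is the worst case, because p(1 − p) is largest there. The same attenuation applied to the Aim 3A correlation takes 0.37 to 0.37/1.068 = 0.346 at d = 0.75, with power 0.86.

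**Step 3: offset associated with HOMA-IR (illustration only).** Let positive φ mean that subjects with higher HOMA-IR are more often on the scanner that reads higher. The observed correlation is

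(−0.324 + d√(p(1 − p))φ) / √(1 + p(1 − p)d² − 2 × 0.324 × d√(p(1 − p))φ).

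With d = 0.5, p = 0.5 and φ = +0.2 this is −0.274/√1.0301 = −0.270 (power 0.66). With φ = −0.2 it is −0.374/√1.0949 = −0.357 (0.88). If the true correlation is zero, the spurious one is 0.05/√1.0625 = 0.049 in size, and the one-tailed error rate rises from 0.05 to about 0.10 when it lies in the hypothesised direction. These are marginal correlations. In the planned model φ would have to remain after adjustment for the listed covariates.

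**Step 4: the change score.** With a constant offset c in CVC on one scanner, (peak + c) − (rest + c) = peak − rest, so c drops out. With a proportional difference g, g × peak − g × rest = g × (peak − rest), so the difference stays. If the resting value came from a structural visit on the other scanner, c would stay too.

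**Step 5: cost of a scanner term.** The Aim 2A model has six covariates (five plus intracranial volume). Going from six to seven, with the partial correlation held at 0.324, changes power from 0.805 to 0.804 by noncentral t, or from 0.737 to 0.729 by the Fisher z approximation.

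**The case against.** The strongest reply is that the loss is small and its cause hypothetical. Both locations are described with the same scanner model, and the research team runs, processes and analyses the scans, which limits an offset without excluding it. The plan does not say that both scanners will be used, and an uneven split costs less than the 50:50 case. All of this stands, and it keeps the point modest.

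Four stronger readings are tempting but not supported:

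- A reader might infer that any scanner offset distorts every CVC analysis. It does not: a constant CVC offset cancels in the change score of Aims 2B and 3B when rest and post-glucose scans come from the visit described in section 4.3.3.c.
- A reader might infer that location is chosen for convenience. No section says how the MRI location is chosen. The space-conflict note in section 4.2 is attached to the exercise core and the Clinical Research Unit, and the scheduling flexibility in section 4.3.3 concerns the order and combining of visits.
- A reader might infer that clinic-recruited subjects with higher insulin resistance would cluster at one scanner and so inflate the false-positive rate. Section 4.1.3 describes mixed recruitment, but nothing links source to scanner. Part of any such link would be absorbed by adiposity and fitness, which are already in the model. In the opposite direction the offset makes the test conservative.
- A reader might infer that baseline and post-glucose scans could be split between scanners. Section 4.3.3.c already puts them in one visit. The only opening is the structural visit in section 4.3.3.b.

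**Conclusion.** The gap is real but limited. Two MRI locations are permitted, and neither design, processing nor model accounts for scanner. The consequence that follows from the documents is added noise in resting CVC (Aims 2A and 3A), if both scanners are used and differ in level. Under the assumed offsets and an even split unrelated to HOMA-IR, Aim 2A loses between about half a percentage point and 5 points of power (0.806 to 0.800 at the low end, 0.754 at the high end), in an aim planned with almost none to spare. Bias in the HOMA-IR coefficient remains a conditional possibility. The change-score aims are exposed only to a proportional scanner difference, or to a resting value taken from another visit. Aim 1 uses no flow or perfusion outcome and is unaffected.

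The case for acting is that the remedy costs almost nothing. It should be pre-specified, because a scanner term added after the results are seen would be a post hoc choice.

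**What to change.** 1. Record the scanner location for every scan.
2. If both scanners are used, add scanner as a covariate in the resting CVC models (Aims 2A and 3A). If all subjects are scanned at one location, the term drops out.
3. For the change in CVC (Aims 2B and 3B), pre-specify a sensitivity analysis with the scanner term.
4. In section 8.3.3, state that the resting value in the change score is the pre-glucose baseline of the OGTT visit, since section 4.3.3.b allows the same sequences at a separate visit.

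The cost is a few lines of SAP text, one field per scan if the location is not already captured, one residual degree of freedom, and under 1 percentage point of power in Aim 2A.

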#### **4.3.4.h. Oral Glucose Tolerance Test (OGTT)**

OGTTs are clinically safe and a minimally invasive procedure to quantify IR. After a minimum 4-hour fast, subjects consume, within 5 min, a beverage containing 75 grams glucose (similar to a can of soda). This is the standard administration of OGTT (Poomthavorn, Nantarakchaikul, Mahachoklertwattana, Chailurkit, & Khlairit, 2013). Blood sampling occurs for 60 minutes (see section [4.3.4.j Blood Sampling](#)). The [name] lab has conducted multiple OGTT studies in IR adults and found the OGTT with MRI measures is well tolerated.

#### **4.3.4.i. Venipuncture**

Only during screening visit. Venipuncture will usually occur in the antecubital fossa or hand by trained personnel using standard aseptic technique.

#### **4.3.4.j. Intravenous Catheter**

Only during MRI-OGTT visit. An IV catheter will be placed by trained personnel in the antecubital fossa or hand using standard aseptic technique. Study staff trained and delegated in phlebotomy/IV placement, WIMR staff, research nurse, or higher study-associated clinical authority (e.g. physician) will insert an IV using standard medical procedures. The IV catheter will remain in place for approximately 2 hours.

#### **4.3.4.k. Blood sampling**

Screening visit:

Approximately 20 mL of blood will be obtained for blood chemistry values.

OGTT-MRI study visit:

Blood draws of approximately 10-15 mL per draw to a cumulative maximum of 100 mL will be obtained via the IV catheter at specific time points to measure blood chemistry values (e.g. insulin, glucose). The specific time points are as follows:

- Baseline
- 5 minutes after OGTT
- 10 minutes after OGTT
- 20 minutes after OGTT

- 30 minutes after OGTT
- 45 minutes after OGTT
- 60 minutes after OGTT

#### 4.3.4.i. Subject Monitoring

During the screening visit, specifically the maximal exercise test, subjects will be monitored for:

- Heart rate (via electrocardiogram or heart rate monitor)
- Oxygen consumption (via mouthpiece or face mask)
- Adverse signs and symptoms

Throughout the OGTT-MRI visit, subjects will be monitored for:

- Blood glucose (via glucometer)
- Heart rate (via electrocardiogram or pulse oximeter)
- Blood pressure (via automated brachial artery auscultation)
- Blood oxygen saturation (via pulse oximeter)
- End-tidal carbon dioxide (via nasal cannula or mask)
- Adverse signs and symptoms

#### 4.3.4.m DEXA Scan

This is for comparison of body composition (amount of body fat and bone density) between subjects. The scanner is a clinical scanner like many hospitals have for measuring body fat and bone density and is operated by a trained researcher.

#### 4.3.5 Summary of Study Visits and Procedures

	Screening Visit	Cognitive Testing Visit	1-hour MRI Visit	OGTT-MRI Visit
Fasting	X	X	X	X
Questionnaires	X	X		
Body Measurements	X			
Blood Draw/IV	X			X
DEXA Scan	X	X (if needed)	X (if needed)	X (if needed)
Exercise Test	X	X (if needed)	X (if needed)	X (if needed)
Cognitive Tests		X		
MRI Scans			X	X
OGTT				X
Vital Signs	X		X	X

#### 4.4. Confidentiality Protections

Risks to confidentiality will be minimized by keeping copies of the documents linking study assignment number and the participant's unique identifiers with the participant's informed consent in locked cabinets of the offices of [name]. Only subject numbers will be used for group assignment, data processing, and analyses. All data will be stored in locked cabinets in a secure lab, and electronic files are all stored on password-protected databases and computers.

Personal information such as name, gender, date of birth, and medication history will be stored in a locked file cabinet in a locked office in the PI's laboratory. Subject information will be coded to remove any personal identifiers during data analysis or research publications. Research oversight and regulatory groups may review study records.

Please see section [7.9.4. Protecting the Confidentiality of Participant Data for more details.](#)

#### 4.5. Remuneration

Subjects will be paid in the following manner:

- Up to \$60 for the screening visit
  - \$20 for completion of the virtual screening procedures
  - \$10 for the blood draw
  - \$10 for the DEXA scan
  - \$20 for the maximal exercise test
- \$60-\$90 for the cognitive visit, prorated at \$30/hr rounded to the nearest half hour
- \$30 for the 1-hour MRI visit, prorated at \$30/hr rounded to the nearest half hour
- \$60 for the OGTT-MRI visit, prorated at \$30/hr rounded to the nearest half hour

The total compensation is estimated to be \$210-\$240 for completing all study visits. Payment will be given to the participant following each visit or sent to the subject's provided address.

## 5. BANKING AND SHARING OF DATA AND BIOSPECIMENS

### 5.1. Data

Blood analysis results and MRI images will be stored for future research use. Banked data will be stored on secure computer servers that are password-protected.

### 5.2. Biospecimens

Blood samples will be stored for future research use. Samples will be stored in temperature controlled locations (e.g. freezer) in a secure location within the Department of Kinesiology.

### 5.3. Assurances

Any data or samples shared with personnel outside of the study team will be coded with a study ID number. Unless the staff is listed as key personnel on this study, they will not be given access to the key linking subject identifiers with their data, samples, or study ID number. The study PI will be responsible for the oversight of the data and sample banking, and will review all requests to utilize the data and samples. The PI will be responsible for confirming that IRB approval or exemption has been granted prior to the release of any data or samples. Future study results obtained from banked data or samples will not be reported to subjects.

As new information about insulin resistance or brain health becomes known, researchers may want to go back and analyze existing data or samples with a different aim. Additionally, combining similar information from multiple studies into a larger set could potentially provide more meaningful information than what was collected in any one study. All new analyses that do not fall under this project's aims or that combine more than one dataset will be approved through the IRB as separate protocols.

